12.1.8.11 Definition of Childbearing Potential and Acceptable Contraceptive Methods

A woman is considered of childbearing potential (i.e., fertile), following menarche and until becoming post-menopausal unless permanently sterile. Permanent sterilization methods include hysterectomy, bilateral salpingectomy, and bilateral oophorectomy.

A postmenopausal state is defined as no menses for > 24 months without an alternative medical cause. A high follicle stimulating hormone (FSH) level in the postmenopausal range may be used to confirm a post-menopausal state in women not using hormonal contraception or hormonal replacement therapy. However, in the absence of > 24 months of amenorrhea, one confirmatory FSH measurement must be obtained or documented.

For female partners of childbearing potential, the following methods of contraception, when used consistently and correctly, are considered reliable for participation of male patients in the study:

- Combined (estrogen and progestogen containing) hormonal contraception associated with inhibition of ovulation: oral, intravaginal, or transdermal
- Progestogen-only hormonal contraception associated with inhibition of ovulation: oral, injectable, or implantable
- Intrauterine device (IUD)
- Intrauterine hormone-releasing system (IUS)
- Bilateral tubal occlusion
- Vasectomized partner (provided that partner is the sole sexual partner and that vasectomized partner has received medical assessment of the surgical success)
- Sexual abstinence (refraining from heterosexual intercourse during the entire study period; the reliability of sexual abstinence needs to be evaluated in relation to the duration of the clinical study and the preferred and usual lifestyle of the patient)

12.1.9 Premedication Regimen

Refer to [Section 10.6](#) for procedures about premedication regimens to prevent infusion associated reactions and gout flare.

12.2 Adverse and Serious Adverse Events

12.2.1 Definition of Adverse Events

Definitions in this section are in accordance with 21 CFR 312.32.

12.2.1.1 Adverse Event (AE)

An AE is any untoward medical occurrence associated with the use of a drug (i.e., study drug) in humans, whether or not considered drug related. An AE can therefore be any unfavorable and unintended sign (including an abnormal laboratory finding), symptom, or disease temporally associated with the use of a drug and does not imply any judgment about causality. An AE can arise with use of any drug or medicinal product. A treatment-emergent AE (TEAE) is an AE that starts or worsens at any time after initiation of study drug on Day 0 of Treatment Period 1 until the End of Study Visit (30 days after completion of the last dose of study drug).

Patients will be considered enrolled in the study upon signing the ICF. During the Screening Phase (from time informed consent is signed to immediately before dosing) any clinically significant changes in the patient's health will be recorded in the patient's medical history and will not be considered as AEs. AEs

 Selecta Biosciences	PHASE 3 STUDY: SEL-212/301 VERSION: 6.1	EFFECTIVE DATE 15 DECEMBER 2022
--	--	--

(and thus SAEs) will be collected from the time the patient is dosed (infusion is started) until the end of the End of Study Visit.

12.2.1.2 Serious Adverse Event (SAE)

An SAE is any AE that occurs irrespective of study treatment assignment, if it satisfies any of these criteria:

- Results in death;
- Is life-threatening;
- Requires inpatient hospitalization \geq 24 hours or prolongs existing hospitalization;
- Results in persistent or significant disability or incapacity or substantial disruption of the ability to conduct normal life functions;
- Is a congenital anomaly or birth defect;
- Is an important medical event that, based upon appropriate medical judgment, may jeopardize the patient or patient may require medical or surgical intervention to prevent one of the outcomes listed above.

12.2.1.3 Suspected Adverse Reaction

A suspected adverse reaction is an AE for which there is a reasonable possibility that the drug caused the AE. For the purposes of IND safety reporting, “reasonable possibility” means there is evidence to suggest a causal relationship between the drug and the AE. Suspected adverse reaction implies a lesser degree of certainty about causality than adverse reaction, which means any AE caused by a drug.

12.2.1.4 Unexpected Adverse Events and Unexpected Suspected Drug Reaction

An AE or suspected adverse reaction (an AE where there is a reasonable possibility that the drug caused the event; suspected drug related) is considered “unexpected” if it is not listed in the SEL-212 Investigator’s Brochure or is not listed at the specificity or severity that has been observed.

12.2.1.5 Infusion Reactions / Adverse Events of Special Interest

A study drug-related AE that occurs within 24 hours after initiation of study drug infusion will be assessed as an infusion reaction. An infusion reaction suspected to be anaphylaxis will be assessed according to the clinical criteria for the diagnosis of anaphylaxis based on the National Institute of Allergy and Infectious Diseases (NIAID) / Food Allergy & Anaphylaxis Network (FAAN) Symposium criteria. ([Sampson 2006](#)).

Infusion reactions will be managed and treated as described below. In addition to premedication with antihistamines and steroids ([Section 10.6.2](#)), the following steps will be implemented in this protocol to either reduce the risk of infusion reactions or manage infusion reactions.

- Patients with prior exposure to uricase therapy will be ineligible
- Patients with a history of anaphylaxis or severe allergic reactions, history of severe atopy, angioedema, or previous infusion reactions will be excluded from the trial.

 Selecta Biosciences	PHASE 3 STUDY: SEL-212/301 VERSION: 6.1	EFFECTIVE DATE 15 DECEMBER 2022
--	--	------------------------------------

- Study drug will be administered at controlled rates only in a healthcare setting and by healthcare providers sufficiently equipped and prepared to manage infusion reactions including anaphylaxis.
- In case of infusion reaction, sites will perform specific assessments as specified in the Study Operations Manual.
- Each patient will be observed for infusion reactions after dosing of study drug in the clinic for approximately 4.5 hours from the start of study drug infusion. Patients will be informed about the signs or symptoms of infusion reactions and will be instructed to notify the Investigator immediately if they believe they are experiencing a reaction.
- Each patient shall remain for a minimum of 1 hour after the completion of infusion of study drug for a period of safety observation.
- All patients will be contacted approximately 24 hours after infusion to determine whether any infusion reaction AEs occurred.
- Patients who experience an infusion reaction will be contacted approximately 24 hours after the event as follow-up.
- Only sites with immediate capability to appropriately respond to a reaction of this severity will be allowed to participate in the trial to reduce the risk to any patient.
- Infusion Reactions (an AESI) will be reported to Parexel Safety in the same manner as SAEs using the same form but ticking the AESI box rather than the SAE box.

Adverse events of special interest (AESI) will be recorded specifically for occurrences of: gout flares, infections, malignancies, viral infections, interstitial lung disease, stomatitis, infusion-related reactions including anaphylaxis, thrombosis (e.g., deep venous thrombosis, pulmonary embolism), and the following laboratory tests, if deemed clinically significant by the PI: hyperlipidemia, worsening of renal function tests, proteinuria, and leukopenia.

12.2.2 Recording Adverse Events

Patients will be encouraged to spontaneously report any changes in health from the time of signing the ICF through completion of the study. Study staff will also inquire about any changes in the patient's health.

All AEs will be recorded in the source document and the CRF. It is the responsibility of the Investigator to review all documentation (e.g., hospital progress notes, laboratory, and diagnostics reports) for the presence of AEs and for a complete evaluation of known AEs.

At minimum for each AE, the Investigator will evaluate and report the event name/term/description, onset (date and time), resolution (date and time), event severity/intensity, relationship to study drug, action taken in regards to study drug, whether the event is an SAE, and whether or not it caused the patient to discontinue the study. The event time is only required while the patient is in the clinic.

During the Screening Phase (from time informed consent is signed to immediately before dosing) any clinically significant changes in the patient's health will be recorded in the patient's medical history and will not be considered as AEs.

12.2.2.1 Adverse Event Term/Name/Description

The Investigator will attempt to establish a diagnosis of each AE based on signs, symptoms, and/or other clinical information. In such cases, the diagnosis will be the AE term used to document the AE/SAE and not the individual signs/symptoms.

12.2.2.2 Relationship to Study Drug

The Investigator is obligated to assess the relationship between study drug and the occurrence of each AE. The Investigator will use clinical judgment to determine the relationship. Alternative causes, such as natural history of the underlying diseases, concomitant therapy, other risk factors, and the temporal relationship of the event to the study drug will be considered and investigated. The Investigator will also consult the SEL-212 Investigator's Brochure and/or Product Information for marketed products in the determination of his/her assessment.

The Investigator will assess causality as to whether the event is related or not related to study drug based on the following definitions:

- Not Related: If no valid reason exists for suggesting a relationship to study drug or the AE was more likely explained by causes other than study drug.
- Unlikely to be Related: Onset of the event has a reasonable temporal relationship to study drug administration and although a causal relationship is unlikely, it is biologically plausible.
- Possibly Related: Onset of the event has a strong temporal relationship to administration of the study drug and a causal relationship is biologically plausible
- Related: The study drug dosing and AE were closely related in time and the AE may be explained by exposure to study product: e.g., known pharmacological effect or recurrence on re-challenge.

There may be situations, particularly when an SAE has occurred, where the Investigator has minimal information to make an assessment in an initial SAE report. However, it is very important that the Investigator always makes an assessment of causality for every SAE prior to transmission of the SAE report. The Investigator may change his/her opinion of causality in light of follow-up information, amending the SAE report accordingly. Any assessment of causality made by the Investigator should also be documented in the patient's source medical record.

12.2.2.3 Adverse Event Intensity/Severity Grading

AEs will be classified according to the Rheumatology Common Toxicity Criteria, version 2.0 ([Woodworth 2007](#)).

- Grade 1 (mild): AE that is usually transient of short duration; or involves mild or minor symptoms which are of marginal clinical relevance; or is asymptomatic consisting of clinical or diagnostic observations alone; no intervention or only minimal treatment with non-prescription intervention was required. The event does not generally interfere with usual activities of daily living.
- Grade 2 (moderate): AE that is usually alleviated with additional specific therapeutic intervention. The event interferes with usual activities of daily living (e.g., shopping, laundry,

transportation, or ability to conduct finances), causing discomfort but poses no significant or permanent risk or harm to the patient.

- Grade 3 (severe): AE that is medically significant/important but not life-threatening; may require brief hospitalization to prevent the event from worsening; interrupts usual activities of daily living, or significantly affects clinical status, or may require intensive therapeutic intervention.
- Grade 4 (life-threatening): An AE, and/or its immediate sequelae, which is associated with an imminent risk of death or which is associated with physical or mental disabilities that affect or limit the ability of a person to perform activities of daily living (eating, ambulation, toileting, etc.); disability may be persistent or result in significant disability, incapacity or limitation of self-care activities.

For an assessment of anaphylaxis, the clinical criteria for the diagnosis of anaphylaxis will be based on the NIAID/FAAN Symposium criteria ([Sampson 2006](#)).

12.2.2.4 Assessment of Outcome

The result or conclusion of the AE will be assessed and recorded by the Investigator as:

- Fatal
- Not recovered/not resolved (the AE has not improved, or patient has not recuperated).
- Recovered/resolved (the AE has improved, or patient has recuperated)
- Recovered/resolved with sequelae (recuperated but retained pathological conditions resulting from the AE)
- Recovering/resolving (the patient is improving but the AE has not yet resolved)
- Unknown (not known, not observed, not recorded, or refused)

12.2.2.5 Action Taken with Study Drug

The action taken regarding study drug will be assessed by the investigator as:

- Dose not changed (dose completed)
- Dose interrupted (IV infusion was temporally modified by temporarily stopping the infusion; slowing of the rate of infusion should also be classified as interrupted)
- Drug withdrawn (IV infusion was modified through termination of the infusion)

A response option for increasing or decreasing the dose is not an available course of action in this study.

12.2.2.6 Laboratory and Diagnostic Abnormalities as Adverse Events

Clinically significant abnormal laboratory findings or other abnormal diagnostic assessments (e.g., ECGs, vital signs) that are detected in dosed patients or that significantly worsen relative to baseline in dosed patients will be reported as AEs. Clinical significance is based on the Investigator's judgment but will typically include findings that result in study withdrawal, result in active management of the patient, or are associated with clinical signs and symptoms. Since the study requires patients with elevated or abnormal sUA levels, abnormal sUA levels will typically not be an AE unless judged by the Investigator as being more severe than expected for the patient.

12.2.2.7 **Pregnancy**

While pregnancy itself is not considered to be an AE, any pregnancy complication or elective termination of a pregnancy for medical reasons will be recorded as an AE and followed. The outcome of all pregnancies must be followed up and documented even if the patient is no longer a study patient.

The Investigator, or his/her designee, will collect pregnancy information on every female who becomes pregnant while enrolled in this study and on every female partner of a male patient who becomes pregnant while the male partner is enrolled in this study. The Investigator will report to the Sponsor or Sponsor's designee within 24 hours of learning of a patient's or female partner of a patient's pregnancy. In the case of a female partner of a male participant enrolled in the study becoming pregnant while the male patient is enrolled in this study, a separate pregnancy partner informed consent form will be completed by the patient's partner. The patient or female partner of a patient must also be followed to determine the outcome of the pregnancy. Information on the status of the mother and child will be forwarded to the Sponsor or Sponsor Designee, as appropriate. Follow-up on the child will be to the first well-child visit. Any premature termination of the pregnancy will be reported.

A spontaneous abortion or congenital abnormalities/birth defects will be considered SAEs and will be reported as such. Furthermore, any SAE occurring as a result of a post-study pregnancy and is considered reasonably related to the study drug by the Investigator, will be reported to the Sponsor.

12.2.3 **Reporting Adverse Events**

12.2.3.1 **Adverse Event Reporting Period**

The study period during which AEs must be reported is from the time the patient is dosed until the 30 (\pm 1) days after the last infusion of study drug. During the Screening Phase (from time informed consent is signed up to the time of dosing) any clinically significant changes in the patient's health will be recorded in the patient's medical history and will not be considered as AEs.

Investigators are not obligated to actively seek AEs or SAEs in former study patients. However, if the Investigator learns of any SAE, including a death, at any time after a patient has been discharged from the study, and he/she considers the event reasonably related to the study drug, the Investigator should promptly notify the Sponsor.

12.2.3.2 **SAE Reporting Procedures**

On discovery, all SAEs should be immediately reported (latest within 24 hours of knowledge of the event) to PAREXEL Safety Services by:

Completing the SAE report form and faxing the documents to PAREXEL Safety Services, using the appropriate regional PAREXEL SAE fax numbers below:

NA (Billerica): [contact]

or

Completing the SAE report form and submitting it to PAREXEL Safety Services via email utilizing the address (es) below:

NA: [contact]

In the event that the site is unable to complete the SAE form to report the event within 24 hours of their knowledge of the event, the investigators may report the SAE over the telephone via the SAE answering service, and then provide the completed SAE form via fax or email. If questions arise regarding the reporting procedures or the specifics of the reporting of an event, sites may call utilizing the following numbers:

NA (Billerica): [contact]

The Investigator will complete the SAE form and provide all case information available at the time of the initial report. The investigator must include the following mandatory case information:

1. The patient identification number
2. The event description
3. The seriousness criteria
4. The Investigator's causality assessment

The reporting Investigator must send the written and signed SAE report by facsimile or email, within 24 hours of observing, notification of, or learning of the SAE to PAREXEL Safety Services as described above. Follow-up information regarding an SAE and the supporting data, including laboratory findings and discharge summaries, should be sent by facsimile or email to PAREXEL Safety Services within 24 hours of receipt of the information.

If the Investigator does not have all information regarding an SAE, the Investigator will not wait to receive additional information before completing as much of the form as possible and notifying the safety group. The form will be updated when additional information is received. The Investigator will always provide at minimum: 1) AE term or event name/description, 2) patient identifier, 3) an assessment of causality ([Section 12.2.2.2](#)).

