7. INVESTIGATIONAL PLAN

7.1 Overall Study Design

This is one of two replicate randomized, double-blind, placebo-controlled, parallel-arm trials to determine the safety and efficacy of two different dose levels of SEL-212 compared to placebo. The study will randomize approximately 120 patients with chronic refractory gout. Approximately 60% of the randomized patients will have tophi at Baseline. Patients, stratified as to the presence or absence of tophi, will be randomized in a 1:1:1 allocation ratio prior to Baseline to receive treatment with one of two dose levels of SEL-212 or placebo every 28 days for approximately 6 months in each trial (SEL-212/301 and SEL-212/302). These two trials will have identical designs with respect to being double-blinded, placebo-controlled as well as identical sample sizes, inclusion/exclusion criteria, efficacy/safety assessments and timing thereof, but will be distinguished by the blinded 6-month extension in SEL-212/301 and that SEL-212/302 will include sites outside of the United States. [REDACTED]

[REDACTED] Efficacy assessments will be conducted at intervals that are appropriate to determine treatment effect with samples for the primary endpoint drawn during Treatment Period 6. Samples will be collected at intervals that are appropriate to determine the uricase activity of SEL-212. Safety will be monitored throughout the study with an independent data safety monitoring board (DSMB). After successful completion of the double-blind treatment phase, patients successfully completing six months in SEL-212/301 will continue, in a blinded fashion, to be treated with the identical investigational treatment (one of two dose levels of SEL-212 or placebo) for 6 additional doses, every 28 days, lasting approximately 6 months. This will provide up to 12 months of continuous treatment with SEL-212 in a placebo-controlled fashion.

The study will be divided into 3 study phases: Screening, Treatment, and Follow-up, described below. The study is depicted schematically in [Figure 1](#).

The total duration of participation in the study will range from approximately 50 to 55 weeks (352 to 383 days) as follows:

- Screening and/or washout and premedication Phase: up to 45 days (up to 6.5 weeks)
- Treatment Phase: 168 days (24 weeks)
- Extension Phase: 168 days (24 weeks)
- Safety Follow-Up: 30 days after last infusion

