7.1.3 Follow-Up Phase

Patients will be followed for safety monitoring (30 + 4 days) after their final study drug infusion and will have an End of Study visit by telephone at the following times: either (1) at completion of the Extension Phase or (2) at early termination if the patient voluntarily withdraws consent. Patients who terminate the study prematurely will continue to be followed by having all Early Termination assessments performed. Patients who terminate the study prematurely who are unable to be on-site for the Early Termination visit will be contacted by telephone for safety follow-up.

If withdrawn from study drug, regardless of reason, the patient will continue study visits to the end of Treatment Period 12.

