8.3.2 Patient Completion

A patient will be considered to have completed the double-blind treatment phase of the study when the patient has completed Day 28 of Treatment Period 6. The patient will be considered to have completed the double-blind extension phase of the study when the patient has completed the Safety Follow-up visit that occurs 30 days (+ 4 day) after the Treatment Period 12 Day 0 visit. Enrolled patients who prematurely discontinue for any reason before completion of the study will be treated as outlined below in [Section 8.3.3.1](#).

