12.1.8.10 Pregnancy Screen

Samples for urine pregnancy testing (hCG) will be obtained.

Male patients of reproductive potential who are having intercourse with female partners of childbearing potential must agree to use 2 forms of contraception, 1 of which must be a barrier method, during the study and for 4 months after the last study drug administration. Acceptable barrier methods include a condom and diaphragm. Acceptable forms of birth control for female partners of childbearing potential are non-hormonal and hormonal intrauterine devices, hormonal birth control pills, hormonal birth control patches, hormonal birth control injections, hormonal birth control implants. Spermicide used alone is not an acceptable method and must be used with another acceptable form birth control method. Abstinence is acceptable if consistent with the patient's normal lifestyle.

Female patients are required to have negative hCG test results throughout the study. If a female patient becomes pregnant after she begins taking study drug, the procedures in [Section 12.2.2.7](#) should be followed.

In addition, for any reported case of delayed menstrual period (over 1 month between menstruations) and for those women with infrequent or irregular menstrual cycles, confirmation of absence of pregnancy should occur.

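### Partner pregnancies have planned collection only while the man is enrolled, so patients dosed through Treatment Period 12 have none for about 72–75% of the 4 post-dose months in which contraception is required

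*Protocol*

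**What the plan says.** Protocol 12.1.8.10 (Pregnancy Screen) requires two forms of contraception, for male patients with partners of childbearing potential, "during the study and for 4 months after the last study drug administration".

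Protocol 12.2.2.7 (Pregnancy) provides for collection of pregnancy information "on every female partner of a male patient who becomes pregnant while the male partner is enrolled in this study". The sentence on the separate partner consent form carries the same enrolment condition.

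Protocol 8.3.2 counts the extension phase as complete "when the patient has completed the Safety Follow-up visit that occurs 30 days (+ 4 day) after the Treatment Period 12 Day 0 visit". Section 7.1.3 agrees: "Patients will be followed for safety monitoring (30 + 4 days) after their final study drug infusion". For patients taken off drug, 7.1.3 adds: "If withdrawn from study drug, regardless of reason, the patient will continue study visits to the end of Treatment Period 12".

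For pregnancies after the study, the one explicit provision in 12.2.2.7 is that the sponsor is told of "any SAE occurring as a result of a post-study pregnancy and is considered reasonably related to the study drug by the Investigator". Section 12.2.3.1 places no duty on sites to look for events in former patients.

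**The concern.** The protocol sets a precaution with a stated duration, then plans to observe the matching outcome for a shorter time. Nothing in the visible text explains the difference.

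The partner route is the main one in this trial. Inclusion criterion 5 admits only women of non-childbearing potential, so the clause on pregnant female patients should rarely apply. In Phase 2 study SEL-212/202, 163 of 170 patients (95.9%) were men.

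What is at stake is the completeness of a small safety dataset. A conception in the second to fourth month after the last dose would reach the sponsor only by chance, or as a serious event that the investigator judged related. Normal outcomes, and adverse outcomes judged unrelated, could go uncounted. There would then be no denominator, and what is collected would depend on a causality judgement. The patients affected are those on drug longest, with up to 12 doses. No efficacy endpoint, estimand or analysis is affected.

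**Working it through.** **Inputs**
- Doses are 28 days apart, 12 in all (Protocol 10.7 and Appendices B and D).
- Screening lasts up to 45 days, and participation totals 352 to 383 days (7.1).
- Follow-up runs 30 to 34 days after the last dose (7.1.3, 8.3.2).
- Contraception runs to 4 months after the last dose (12.1.8.10).
- Assumption: 4 months is 120 to 121.75 days, because the documents give no day count.

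**Reproducing the plan's own figure.** The last dose falls on day 11 × 28 = 308. Adding 30 days gives day 338, and 45 days of screening gives 383 days, or 383/7 = 54.7 weeks. This matches the stated maximum and confirms that participation ends about 30 days after the last dose.

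**Share of the post-dose months without planned collection**, (M − F)/M, where M is the 4 months in days and F is follow-up after the last dose:

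| M (days) | F = 30 | F = 34 |
|---|---|---|
| 120 | 90/120 = 75.0% | 86/120 = 71.7% |
| 121.75 | 91.75/121.75 = 75.4% | 87.75/121.75 = 72.1% |

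The gap is about 86 to 92 days, or 72–75%.

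**Share of the contraception period from first dose**, (M − F)/(308 + M):
- M = 120: 90/428 = 21.0% and 86/428 = 20.1%.
- M = 121.75: 91.75/429.75 = 21.3% and 87.75/429.75 = 20.4%.

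The range is about 20–21%.

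**Patients who stop drug early but stay to the end of Treatment Period 12 (day 336)**, on the nominal calendar with M = 121.75:

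| Last dose in | Day of last dose | Days observed after it | Uncovered |
|---|---|---|---|
| TP11 | 280 | 56 | 54% |
| TP10 | 252 | 84 | 31% |
| TP9 | 224 | 112 | 8% |
| TP8 or earlier | 196 or earlier | 140 or more | 0% |

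**How many men.** At 163/170, 120 patients would include about 115 men. One third of patients are on placebo, which leaves 80 × 163/170 ≈ 77 men on SEL-212. The documents do not say how many will be dosed to Treatment Period 12. As a rough illustration only, using the assumed 45% response rate as a stand-in for staying on drug gives 80 × 0.45 × 0.959 ≈ 35, before any losses in the extension. The share with partners of childbearing potential is not given, and men up to age 80 are eligible.

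**The case against.** The strongest reply is that 12.2.2.7 is wider than its collection clause. The sentence requiring a report within 24 hours of learning of a pregnancy has no enrolment limit. The sentence on following pregnancy outcomes has none either, and expressly reaches patients who have left the study. The sentence making spontaneous abortion and birth defects serious events has no causality filter. On that reading, a late partner pregnancy that a site learns of is reportable whatever its cause.

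Much of this stands. A reader might infer that reporting after exit is excluded; the text does not support that. But these sentences apply only once someone knows of the pregnancy. None sets a period for detecting one or requires anyone to ask. Partner consent stays tied to enrolment, and the only sentence that names post-study pregnancies is restricted to related serious events. At best the section is ambiguous about known pregnancies, and it plans no detection of unknown ones.

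A second reply is that instructions to report later pregnancies may sit in the consent form or the Study Operations Manual. Neither is available here, so this cannot be excluded. The protocol section would still need to agree with them.

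A third is that few events are expected. That is probably right and keeps the point minor, but the number cannot be worked out from the documents.

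**Conclusion.** The mismatch between 12.1.8.10 and 12.2.2.7 is real, and correcting it is a cheap improvement. For patients dosed through Treatment Period 12, about 72–75% of the 4 post-dose months has no planned collection of partner pregnancies. This rests on 4 months being 120–122 days and on enrolment ending at the 30 to 34 day follow-up. The gap shrinks to nothing for patients who stop by Treatment Period 8 and stay in the study. Placebo patients have no exposure to SEL-212.

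Three stronger readings are tempting and are not supported:
- **Three quarters of the whole contraception period is unobserved.** That period also covers the study itself. Counted from first dose, the uncovered share is about 20–21%.
- **The protocol declares a reproductive risk lasting 4 months.** Section 12.1.8.10 sets a precaution and gives no mechanism or rationale. Nothing here says whether 4 months is the right length.
- **About 115 men are exposed and unobserved.** That count includes the placebo arm and patients who stop early and remain in follow-up.

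**What to change.** Reconcile 12.2.2.7 with 12.1.8.10:

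1. Change the enrolment condition in two places, the male-partner part of the collection clause and the partner-consent sentence. Suggested wording for both: *while the male patient is enrolled and until the end of the post-dose contraception period in Section 12.1.8.10, whichever is later*. The last three words keep the longer cover that early stoppers already have. Changing only the collection clause would leave late partners with no consent route. The similar phrase for female patients is a different clause and is not the one to edit.
2. State that these pregnancies and their outcomes are reported regardless of causality.
3. Add a reminder to the End of Study telephone call already scheduled (7.1.3, Appendices A and C), asking male patients to report any partner pregnancy in that period.

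Apply this to all arms, since sites are blinded.

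The cost is a short amendment, an IRB-approved wording change to the partner consent form, and occasional reports after a patient's last contact. No visits, samples or analyses are added.
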